8.6.2.4 Subgroup analyses for secondary efficacy variables

Subgroup analysis will be done for all three secondary endpoints using the same subgroups as described in Section 8.6.1.6. The subgroup analyses for the secondary endpoints will be done on the mITT analysis set only. The same type of models as used for the secondary endpoints will also be fit separately for each level of the subgroup.

8.6.3 Other Efficacy Variable(s)

All other efficacy variables will be analyzed on mITT analysis set, if not specified otherwise. Tabulation by subgroups, where noted, is referring to the subgroups as specified for the subgroup analysis of primary and secondary efficacy variables.

CeD PRO non-GI Domain Scores (Headache and Tiredness Items)

Change from baseline through Week 24 in the CeD PRO non-GI domain scores (headache and tiredness items) will be tabulated by treatment group and by time point, both overall and by subgroups.

Mean change from baseline by treatment group and time point will be plotted, both overall and by subgroups.

CeD PRO Nausea Domain Scores

Change from baseline through Week 24 in the CeD PRO Nausea domain score will be tabulated by treatment group and time point, both overall and by subgroups.

Mean change from baseline by treatment group and time point will be plotted, both overall and by subgroups.

CeD PRO Symptomatic and Asymptomatic Days

Symptomatic (Score of greater than 0) and asymptomatic (Score of 0) days will be assessed in terms of the Abdominal Symptoms domain, Diarrhea and Loose Stool Domain, and Total GI score of the CeD PRO in a binary way.

In order to make the post-baseline number of symptomatic and asymptomatic days comparable with the baseline, the ratio of the total numbers to the overall number of days and the ratio of monthly numbers to the total number of days at each month through Week 24 will be summarized for each domain. Other cut off points for symptomatic scores including Score of ≥ 2 or Score of ≥ 3 in the domain scores will be evaluated.

MMRM analysis will be performed to assess changes from baseline through Week 24 on monthly totals of symptomatic days for each domain, with treatment, week, and week by treatment as fixed effects, the continuous baseline Abdominal Symptoms domain score and VH:CD ratio as covariates, and subject as a random effect. The model will be similar to that of the primary model.

Percent Change from Baseline in CeD PRO Domains

Percent change from baseline through Week 24 in the Abdominal Symptoms domain, the Diarrhea and Loose Stool domain, and the Total GI score of the CeD PRO will be summarized by treatment group and time point.

Proportion of Subjects Who Reach 30% and 50% Reduction in CeD PRO Domains

Subjects who reach a 30% and 50% reduction from baseline in the Abdominal Domain, Diarrhea and Loose Stool Domain, and Total GI score of the CeD PRO scores will be tabulated by counts and proportions for each week of the study, including tabulation overall and by subgroup. The proportions of these subjects at Week 24 will be analyzed with a chi-square test.

Weekly Worst Symptom Domain Score in CeD PRO

Absolute change from baseline through Week 24 in weekly worst symptom domain score for each of the following three domains (1) Abdominal Symptom domain, (2) Diarrhea and Loose Stool domain, and (3) Total GI score of the CeD PRO will be analyzed in a similar manner to that of the

primary endpoint, by using MMRM model with treatment, week, and week by treatment as fixed effects, the continuous baseline Abdominal Symptoms domain score and VH:CD ratio as covariates, and subject as a random effect.

The absolute values and change from baseline values (absolute and percent) will also be summarized by treatment group and time point.

Mean change from baseline of weekly worst symptom domain score will be plotted by treatment and time point for each domain.

BSFS Weekly Stool Frequency Type 6 or 7

Absolute change from baseline through Week 24 in total weekly stool frequency (sum of daily frequencies) for stools that are Type 6 or 7 based on the BSFS will be tabulated by treatment group and week. For imputation rules refer to Section 8.2.3.

Mean change from baseline of total weekly stool frequency of BSFS Type 6 or 7 will be plotted by treatment and time point.

Gluten-Induced Serum Antibodies

Absolute change from baseline through Week 24 will be tabulated by treatment group and time point (both overall and by subgroup) in the following gluten-induced serum antibodies for subjects who had all their samples analyzed through ELISA methods:

- Anti-tissue transglutaminase antibodies (anti-tTG) IgA
- Anti-deamidated gliadin peptide (anti-DGP) IgA

Anti-tTG IgG and Anti-DGP IgG are only collected at Screening and will be summarized as part of Baseline Characteristics.

Investigator Global Assessment (IGA)

The IGA is a 5-point Likert scale designed for use by the Investigator or qualified sub-investigator to assess the subject's clinical disease activity (Inactive Disease, Mild Disease, Moderate Disease, Severe Disease, Very Severe Disease) at each specified time point. Absolute change from baseline to worst post-baseline IGA through Week 24 will be tabulated by treatment group in a shift table. Additionally, this table will be repeated for each subgroup.

Patient Global Impression of Change (PGIC)

Subjects will be asked to complete the PGIC every 2 weeks in the eDiary, beginning 2 weeks after the first dose of placebo, at Visit 1. Subjects will be asked to compare their symptoms to those before treatment as follows:

"Please choose the response below that best describes the overall change in your celiac disease symptoms since you started taking the study medication: Much better, A little better, No change, A little worse, Much worse."

The qualitative responses will be scored quantitatively as 1 = Much better, 2 = A little better, 3 = No change, 4 = A little worse, 5 = Much worse for analysis.

Absolute change from baseline in PGIC through Week 24 will be tabulated by treatment and time point. Additionally, this table will be repeated for each subgroup.

Patient Global Impression of Severity (PGIS)

Subjects will be asked to complete the PGIS every 2 weeks in the eDiary, from the evening of eDiary dispensation at Visit 1 (Day -28) through the end of the study. Subjects will be asked to assess the severity of their symptoms as follows:

"Please choose the response that best describes the severity of your celiac disease over the past 7 days (check one response): None, Mild, Moderate, Severe, Very Severe."

The qualitative responses will be scored quantitatively as 1 = None, 2 = Mild, 3 = Moderate, 4 = Severe, 5 = Very Severe for analysis.

Absolute change from baseline in PGIS through Week 24 will be tabulated by treatment and time point. Additionally, this table will be repeated for each subgroup.

PROACTIVE Dietary Questionnaire

The dietary questionnaire relates to subject's celiac disease during the past 7 days. Subjects will answer the following two questions weekly from Visit 1:

- How many days did you consume a meal prepared outside of your home?
- How many days do you think you consumed gluten?

The results will be summarized by treatment group and week based on the visit windowing for the PROACTIVE Dietary Questionnaire. The results will also be presented in a data listing.

Impact of Celiac Disease Symptoms Questionnaire (ICDSQ)

The ICDSQ questionnaire is an instrument developed by Alvine Therapeutics to assess the impact of celiac disease symptoms on patients' quality of life (Acaster and Acaster, 2011).

For each question, the qualitative assessments will be scored quantitatively as 1 = Not at all, 2 = A Little, 3 = Moderately, 4 = Very Much, 5 = Completely for analysis.

Absolute change from baseline through Week 24 in domains of the ICDSQ (Daily Activities, Social Activities, Emotional Well-Being, Physical Activities) and Total score will be summarized by treatment and time point.

The scoring of the ICDSQ domains (ICDSQ Scoring Manual v1.0, April 2022) is as follows:

- Daily Activities: Mean of Items 1 through 4
- Social Activities: Mean of items 5 through 7
- Emotional Well-Being: Mean of items 8 through 12
- Physical Activities: Mean of items 13 and 14

The total ICDSQ score is calculated as the sum of the four domain scores.

EQ-5D-5L

The EQ-5D-5L is a 6-item, self-administered generic measure of health status and consists of two parts: a descriptive system and a visual analog scale (VAS).

Absolute change from baseline through Week 24 in EQ-5D-5L (VAS score) will be tabulated by treatment group and time point, both overall and by subgroups.

Descriptive system items will be listed.

Disease Activity Biomarkers

Blood samples to analyze biomarkers of disease activity (e.g., serum IL-15) will be collected prior to treatment administration on visits 3, 5, 7, 9, 11, 13, 15 and 16. Absolute change from baseline through Week 24 in biomarker of disease activity (serum IL-15) will be tabulated by treatment group and time point.

Small Bowel Mucosal Architecture as Assessed by VH:CD Ratio

EGD and biopsy are performed at visits 2 and 15. Villus height (VH, in micrometers) and crypt depth (CD, in micrometers) and their ratio, VH:CD will be assessed. Absolute change from baseline to Week 24 in small bowel mucosal architecture, as assessed by the change in VH:CD in intestinal biopsies will be tabulated by treatment group. Additionally, tabulations of proportion (%) of subjects with VH:CD <2 and ≥2 at baseline and end of study will be provided.

Marsh-Oberhuber Histology Score

The Marsh-Oberhuber histology score (M0, M1, M2, M3a, M3b, or M3c) will be assigned from EGD biopsy samples collected at visits 2 and 15. The Marsh-Oberhuber histology scale will be assessed as frequencies and proportions. Frequencies will be tabulated for each category on the scale, along with respective change from baseline in a shift table.

Additionally, a 3-category outcome will be derived, in which subjects are categorized as having worsening scores from baseline, no change from baseline, and those with improvement from baseline. Marsh score of 0 is considered the best and Marsh score of 3c is considered the worst. Any score shifts in the direction from 0 towards 3c (e.g. 0 to 1 or 3a to 3b) is considered worsening. On the other hand, any score shifts from the direction from 3c to 0 is considered as improvement (e.g. 3c to 3b, or 2 to 0 is considered improvement).

The 3-category outcome will be summarized by treatment group. The Cochran–Mantel–Haenszel test (CMH) (using modified ridit scores for the 3-level outcome), stratified by baseline Marsh-Oberhuber score (M0, M1, M2 vs. M3a, M3b, M3c) will be used to assess differences between active and placebo treatments in this 3-category outcome.

Adherence to GFD

The G12 antibody-based stool and urine gluten tests are validated assays used to assess patient compliance with gluten challenge and to measure possible gluten contamination.

The G12 stool test and urine gluten test results (positive/negative) will be presented by treatment group and visit. Additionally, an overall summary of subjects will be generated, cross-tabulating the baseline test result (positive/negative) with having at least one post-baseline test (positive/negative), separately for urine and stool tests.

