Symptomatic days will be assessed in terms of the Abdominal Domain, Diarrhea and Loose Stool Domain, and Total GI score of the CeD PRO. A given day is defined as a symptomatic day if any of the domain scores is >0. A day is considered asymptomatic if all of these scores are 0. The number of symptomatic days and asymptomatic days will be derived by month (including baseline) [based on month-based visit windows defined below] and total during the double-blind treatment period (through Week 24).

Weekly Worst Symptom Domain Score in CeD PRO

Weekly worst symptom domain scores will be derived separately for each of the following three domains: 1) Abdominal Domain score, 2) Diarrhea and Loose Stool Domain score, and 3) Total GI score by selecting the worst daily score for all items within each domain for a given week (based on analysis visit windows defined below) and averaging these scores.

BSFS Stools of Type 6 or 7

The BSFS is a pictorial aid to help subjects identify the shape and consistency of their stools during the study (Riegler et al, 2001). The subject will be asked to record the number of stools that have a consistency of Type 6 or 7 (loose stool or entirely liquid) at bedtime daily in the eDiary. On the days in which the subject experiences no such stool (BSFS Type 6 or 7), the subject should record 0 in the eDiary instead of leaving it blank. The sum of weekly stool frequency (sum of the previous 7 days) through Week 24 for stools of BSFS Type 6 or 7 will be calculated, based on the analysis visit windows (defined below). In case of multiple records for stool in one day the latest record in time will be considered.

Baseline Value for Patient-Reported Assessments captured in eDiary

In general, the last non-missing value prior to the first dose of double-blind treatment will be used as the baseline value.

For patient-reported assessments captured in the eDiary, the following definitions of baseline in Table 2 will be used:

Table 2. Definition of Baseline for Patient-Reported Assessments Captured in eDiary

Assessment	Baseline Definition				
CeD PRO (Abdominal domain and other weekly domain scores)	Average of scores from 7 days prior to randomization (e.g., last week of placebo run-in).				
BSFS	Sum of Type 6 or 7 stool experienced over the 7 days prior to the date of first dose of double-blind treatment.				
PGIC/PGIS	Most recent assessment prior to the first administration of double-blind treatment.				

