PROACTIVE Dietary Questionnaire	Most recent assessment prior to the first administration of double-blind treatment.				

Visit Windowing (post-baseline) for Patient-Reported Assessments captured in eDiary

Analysis visit windows will be applied for following patient-reported eDiary assessments for postbaseline visits and are described below:

- CeD PRO
- BSFS
- PGIS/PGIC
- Weekly Diet Questionnaire

CeD PRO analysis visit windows (for week-based analysis).

In case of missing visit, the prior visit + 14 days will be taken.

Period	Analysis Visit	Days included in analysis window
Double-blind treatment	Week 2	Days -7 to -1 prior to actual Visit 4 date
Double-blind treatment	Week 4	Days -7 to -1 prior to actual Visit 5 date
Double-blind treatment	Week 6	Days -7 to -1 prior to actual Visit 6 date
Double-blind treatment	Week 8	Days -7 to -1 prior to actual Visit 7 date
Double-blind treatment	Week 10	Days -7 to -1 prior to actual Visit 8 date
Double-blind treatment	Week 12	Days -7 to -1 prior to actual Visit 9 date
Double-blind treatment	Week 14	Days -7 to -1 prior to actual Visit 10 date
Double-blind treatment	Week 16	Days -7 to -1 prior to actual Visit 11 date
Double-blind treatment	Week 18	Days -7 to -1 prior to actual Visit 12 date
Double-blind treatment	Week 20	Days -7 to -1 prior to actual Visit 13 date
Double-blind treatment	Week 22	Days -7 to -1 prior to actual Visit 14 date
Double-blind treatment	Week 24	Days -7 to -1 prior to actual Visit 15 date

CeD PRO analysis visit windows (for month-based analysis of symptomatic days)

Period	Month	Days included in analysis window
Run-in	Baseline	Days -28 to -1 prior to Actual Visit 3 date
Double-blind treatment	1	Actual Visit 3 date (inclusive) through day prior to actual Visit 5 date if available, or Visit 3 date + 28 days (if Visit 5 is missing)
Double-blind treatment	2	Actual Visit 5 date (inclusive) through day prior to actual Visit 7 date if available, or Visit 5 date + 28 days (if Visit 7 is missing) or Visit 7 – 28 days if Visit 5 is missing
Double-blind treatment 3		Actual Visit 7 date (inclusive) through day prior to actual Visit 9 date if available, or Visit 7 date + 28 days (if Visit 9 is missing) or Visit 9 – 28 days if Visit 7 is missing
Double-blind treatment	4	Actual Visit 9 date (inclusive) through day prior to actual Visit 11 date if available, or Visit 9 date + 28 days (if Visit 11 is missing) or Visit 11 -28 days if Visit 9 is missing

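### The exploratory symptomatic-days MMRM is fitted to raw monthly counts, so a post-baseline fall in diary completion or a mid-month dropout is scored as improvement

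*SAP*

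**What the plan says.** **Definition of a symptomatic day (SAP 8.2.2.1).** "A given day is defined as a symptomatic day if any of the domain scores is >0". An asymptomatic day needs all the scores to be 0. Both definitions need a recorded score, so a day without an entry is neither.

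**Monthly derivation (SAP 8.2.2.1).** "The number of symptomatic days and asymptomatic days will be derived by month". The baseline month is fixed: "Days -28 to -1 prior to Actual Visit 3 date". Later months run from one actual visit date to the day before another. If the closing visit is missing there is a fallback, which for Month 1 reads "Visit 3 date + 28 days (if Visit 5 is missing".

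**Summary (SAP 8.6.3).** The text begins "In order to make the post-baseline number of symptomatic and asymptomatic days comparable with the baseline, the ratio of the total numbers" and continues that "the ratio of monthly numbers to the total number of days at each month through Week 24 will be summarized for each domain".

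**Model (SAP 8.6.3).** The next paragraph says "MMRM analysis will be performed to assess changes from baseline through Week 24 on monthly totals of symptomatic days for each domain". Terms and covariates follow the primary model. No offset or denominator is given.

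**Missing-day rules elsewhere.** Weekly CeD PRO scores need at least 4 daily scores (SAP 8.2.2.1). Weekly stool sums need 4 days, and the missing days are imputed from the recorded ones (SAP 8.2.3). No corresponding rule is given for monthly counts. SAP 8.2.4 keeps data from subjects who leave up to the point of leaving, and nothing covers a partial month.

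**The concern.** The SAP recognises that raw numbers of symptomatic days are not comparable with baseline, then fits its only specified model for these days to the raw numbers. An incomplete month enters that model as an observed low value, not as a missing one, so the missing-at-random handling in the MMRM does nothing for it.

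Incomplete diaries are a documented fact in this trial. SAP 8.6.1.5 reports that some subjects did not fill in the questionnaire every day in the week before randomization, and adds a sensitivity analysis of the primary model for that reason. Monthly counts have no such protection.

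The stakes are moderate. The variable is exploratory, but SAP section 7 says that the choice of endpoints and dose for later confirmatory studies will draw on all the evidence, and the test is run at two-sided 0.05 without multiplicity adjustment. A spurious signal here could be read as support for a dose. Change within an arm is distorted even when the arms behave alike.

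**Working it through.** The plan states no power or precision figure for this variable, so there is none to reproduce.

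**Inputs from the documents.** Baseline is 28 days. Visits 3, 5, 7, 9, 11, 13 and 15 fall on Days 1, 29, 57, 85, 113, 141 and 169, so each nominal month has 28 days. The windows are +2 days at Visit 3 and ±2 days afterwards. About 55 subjects are planned per arm.

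**Assumptions (not in the documents).** The share of days that are symptomatic, p, is 0.6 to 1.0 and does not change. Diary completion is 80-95% and dropout 10-20%.

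**Step 1: change within a subject.** With completion c, the expected count in a 28-day month is 28 x c x p. The expected false change is 28 x p x (c_post - c_base).
- c_base = 1.00, c_post = 0.90, p = 1: -2.8 days.
- c_base = 0.90, c_post = 0.90: 0.
- c_base = 0.90, c_post = 1.00, p = 1: +2.8 days, an apparent worsening.

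Single-month effects relative to a complete baseline:

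| Event in one month | Formula | p = 0.8 | p = 0.6 to 1.0 |
|---|---|---|---|
| 3 missed days | -3p | -2.4 | -1.8 to -3.0 |
| 7 missed days | -7p | -5.6 | -4.2 to -7.0 |
| Dropout after day 14 | -14p | -11.2 | -8.4 to -14.0 |

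**Step 2: difference between arms.** With equal baseline completion, the false difference is 28 x p x (c_active - c_placebo). For 90% against 95% it is 28 x 0.6 x (-0.05) = -0.84 up to 28 x 1.0 x (-0.05) = -1.4 days per month. If completion changes equally in both arms, the difference is 0.

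**Step 3: month length.** At the widest, Month 1 spans 24 to 30 days and Months 2-6 span 24 to 32. A 24-day month gives -4p (-2.4 to -4.0) and a 32-day month +4p (+2.4 to +4.0). Months share boundaries, so a late visit lengthens one and shortens the next. With all boundary visits attended, the total runs from 167 - 3 = 164 to 171 - 1 = 170 days, which is 27.3 to 28.3 days per month on average.

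**Step 4: illustrative null simulation.** Settings: 55 per arm, 6 months, mean p = 0.8 (beta-distributed), 95% baseline completion and 400 runs. A t-test on subject-mean change stands in for the overall MMRM contrast. Month lengths were drawn independently from 24 to 32 days, which exaggerates that noise.

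| Completion, placebo / active | Dropout, placebo / active | Counts: false difference (days/month) | Counts: rejection | Ratio: rejection |
|---|---|---|---|---|
| 90% / 90% | 10% / 10% | -0.02 | 5% | 2% |
| 95% / 90% | 10% / 10% | -1.1 | 49% | 5% |
| 95% / 85% | 10% / 10% | -2.3 | 95% | 6% |
| 90% / 90% | 10% / 20% | -0.34 | 8% | 3% |

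The ratio is symptomatic days over recorded days, rescaled to 28. Its false difference lay between -0.05 and +0.03 days in every row. The Monte Carlo standard error at 5% is about 1 point (√(0.05 x 0.95 / 400) = 0.011).

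**The case against.** The best defence is that the variable is exploratory, the trial is double-blind, and the ratios would be reported beside the test. The primary and secondary CeD PRO endpoints use weekly means under the 4-day rule and do not share the fault. Nothing in the documents shows completion differing between arms, and with equal completion and dropout the comparison is unbiased. All of this stands, and it limits the size of the point. It does not justify testing the quantity that the SAP considers not comparable. The descriptive ratio may not help either: its denominator is not defined, and if it means calendar days, missed days still dilute the share.

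Four stronger readings are tempting, and the documents do not support them.
- **Short visit months favour improvement.** Months can be long as well as short, and the lengths nearly cancel over the six months (Step 3).
- **The fallback is a 29-day error.** Counted inclusively, visit + 28 days does give 29 days. It can equally be read as a stand-in for the missing visit date, with the month ending the day before, which gives 28. The companion fallback that counts back 28 days from the closing visit also gives 28. Even 29 days would add p days (0.6 to 1.0) in the direction of worsening.
- **Imperfect completion always yields false benefit.** The -2.8 days at 90% requires perfect completion at baseline, and SAP 8.6.1.5 reports missed diary days in the last run-in week.
- **Dropout has a large effect on the trial result.** The -14 days is one subject in one month. Doubling dropout in one arm moved the arm comparison by only -0.34 days per month, and subjects who stop treatment are encouraged to keep attending.

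**Conclusion.** The point holds for the exploratory symptomatic-days model. Fitting raw monthly counts confuses symptom-free days with days that have no entry, and no rule elsewhere in the SAP corrects this. Falling completion after baseline and mid-month dropout push towards apparent improvement, and missed baseline days push the other way.

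The arm comparison is biased only if the change in completion, or dropout, differs by arm. Under the assumed 5-point gap the false difference is about 0.8 to 1.4 days per month, and at p = 0.8 that was enough to reject a true null in about half of the simulated trials. The size scales with p, so a stricter symptom cut-off, such as the scores of 2 or 3 that SAP 8.6.3 also mentions, would usually shrink it. Completion, dropout and symptom share are all assumptions. A month with no entries at all is undefined in the SAP (zero or missing), and the conclusion does not depend on it.

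**What to change.** 1. Fit the MMRM to symptomatic days divided by recorded diary days in the month, multiplied by 28 if a day scale is wanted. Derive baseline in the same way.
2. Define the denominator of the descriptive ratio as recorded diary days.
3. Set a month to missing below a prespecified minimum. Sixteen of 28 days matches the weekly rule (4/7 x 28 = 16). Another threshold is defensible if it is fixed before unblinding.
4. State that the missing-visit fallback ends the day before visit + 28 days, so that it spans 28 days and adjoining months cannot share a day.

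The cost is SAP wording and one derived variable, with no new data. Some sparse months become missing, which the MMRM then handles under its missing-at-random assumption. The ratio still assumes that skipped days resemble recorded days within the month. That is weaker than the present rule, under which a skipped day never counts as symptomatic.

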8.2.1 Descriptive Statistics

For continuous variables, the following descriptive statistics will be provided, unless stated otherwise: number of non-missing observations (n), number of missing observations (nMiss), mean, median, standard deviation (SD), minimum, maximum, Q1 and Q3 quartiles. Additional statistics will be provided for PK-related data, including the geometric mean (mean_{geo}) and geometric CV% (CV%_{geo}).

For categorical variables, number of non-missing observations and frequency with percentage per category will be displayed. Denominators for percentages are the number of subjects with non-missing values in the pertinent analysis set and treatment group as appropriate, unless otherwise specified.

The number of missing observations (nMiss) is displayed only if > 0. For continuous variables it is displayed after the number of non-missing observations, for categorical variables it is displayed last in category.

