 stderr stderr;
   ods output parameterestimates=midiff;
run;
Analysis of covariance (ANCOVA)
(IEL Density)
proc glm data = data alpha=0.05 outstat = F tests;
   class TRT(ref='Placebo');
   model CHANGE = TRT BASEABD BASEVHCD/ clparm solution SS1 SS2;
   estimate "PRV-015 100 mg vs Placebo" TRT 1 0 0 -1;
   estimate "PRV-015 300 mg vs Placebo" TRT 0 1 0 -1;
   estimate "PRV-015 600 mg vs Placebo" TRT 0 0 1 -1;
   1smeans TRT /cl stderr alpha=0.05 pdiff = all;
   ods output ParameterEstimates=Par est LSMeanCL=LS meanCL
      LSMeans=LS mean OverallANOVA=ANOVA Estimates=Eff est;
run;
Levene's test
proc glm data = data alpha = 0.05;
 class TRT;
  model CHANGE = TRT / clparm solution SS1 SS2;
   means TRT / hovtest;
   ods output HOVFTest = Levene;
run;
```

Chi-square test:

```
proc freq data = data;
  tables TRT*REDUCBLX / chisq;
  output out=CHiSqData pchi;
```

run;

where REDUCBLX shows if subject had X% reduction from baseline at Week 24.

The Cochran-Mantel-Haenszel test (CMH)

```
proc freq data=data;
  tables BLMED*TRT*RESPONSE / cmh scores=modridit;
  output out=outdata;
run;
```

where BLMED is baseline Marsh-Oberhuber score (M0, M1, M2 vs. M3a, M3b, M3c) score and RESPONSE shows if subjects have worsening scores.

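### The Week 24 responder test and the Marsh test are each coded as one four-arm test, so neither compares a dose with placebo, and the responder test also leaves out the randomisation factors

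*SAP*

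**What the plan says.** **Responders.** SAP 8.6.3 tabulates subjects reaching 30% and 50% reduction in three CeD PRO scores (Abdominal, Diarrhea and Loose Stool, Total GI) by week, overall and by subgroup. On testing it says: "The proportions of these subjects at Week 24 will be analyzed with a chi-square test". The code in SAP 11.4 is "tables TRT*REDUCBLX / chisq", with the note "where REDUCBLX shows if subject had X% reduction from baseline at Week 24". It has no stratum variable and no WHERE or BY statement to form pairs of arms.

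**Marsh.** SAP 8.6.3 defines a three-level outcome (worse, unchanged, improved). It says that a CMH test with modified ridit scores, stratified by baseline Marsh grade (M0 to M2 against M3a to M3c), "will be used to assess differences between active and placebo treatments in this 3-category outcome". The code is "tables BLMED*TRT*RESPONSE / cmh scores=modridit", again on all arms. The note under it ends "and RESPONSE shows if subjects have worsening scores", which describes a two-level variable.

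**Design.** Protocol 4.2 says the dose-ranging design was chosen to compare each regimen separately with placebo and to select a dose or doses. SAP 5 randomises 1:1:1:1, stratified by VH:CD (<2, ≥2) and baseline Abdominal score (<3, ≥3).

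**General rules.** SAP 8.2 sets two-sided 0.05 tests without multiplicity adjustment, says that 95% confidence intervals will be constructed, and allows the appendix code to be modified without a SAP amendment.

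**The concern.** A dose-ranging trial needs each dose set against placebo. A four-arm chi-square tests whether all four rates are equal. When it rejects, the cause may be a difference between two active doses; when it does not, one effective dose may have been diluted by two ineffective ones. It gives no effect estimate or interval.

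For responders, the SAP text names no comparison that would override the code. For Marsh, text and code conflict. The pattern is particular to these two tests: in the same appendix the IEL ANCOVA has an explicit contrast for each dose against placebo, and the MMRM code requests differences between LS means.

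The responder test also omits the factors used to balance the arms, whereas the MMRM and ANCOVA models adjust for baseline Abdominal score and VH:CD.

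At stake is how these results feed dose selection, which SAP 7 rests on the totality of evidence. If the comparison is left open, it can be chosen after the data are seen.

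**Working it through.** **The plan's own figures.** The documents give no power, rate or sample size for either test. The 80% power in SAP 7 (50 evaluable per arm, difference 0.40) belongs to the primary endpoint. Its SD is redacted, so it cannot be reproduced independently, and it does not bear on this point. From the documents I take only n = 50 per arm and two-sided 0.05. All response rates and counts below are assumptions.

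**Degrees of freedom as coded.**
- Responders: 4 arms × 2 outcomes gives (4−1)(2−1) = 3 df.
- Marsh: 4 arms × 3 categories gives row-mean-scores 3 df and general association (4−1)(3−1) = 6 df. The 1-df correlation statistic is a trend over the arm order. None is a dose-placebo contrast, and the SAP does not say which will be reported.

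**Two examples.** Four-arm X² = Σ(xⱼ − n·p̄)² / [n·p̄(1−p̄)]. Both examples have 71 responders in 200, so p̄ = 0.355, n·p̄ = 17.75, and the denominator is 50 × 0.355 × 0.645 = 11.449. Pairwise X² = d² / [q(1−q)·2/50], where d is the difference in proportions and q the pooled proportion.

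| Responders (placebo/100/300/600 mg) | Four-arm X² (3 df) | p | Each dose vs placebo, p |
|---|---|---|---|
| 15/16/15/25 | 70.75/11.449 = 6.18 | 0.103 | 0.83, 1.00, 0.041 |
| 18/10/18/25 | 112.75/11.449 = 9.85 | 0.020 | 0.075, 1.00, 0.157 |

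For 600 mg in the first row: d = 0.20, q = 0.40, X² = 0.04/0.0096 = 4.17. In the second row: d = 0.14, q = 0.43, X² = 0.0196/0.009804 = 2.00. The second four-arm result is driven by 100 mg against 600 mg.

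**Power, 50 per arm** (noncentral chi-square and 100,000 simulations, except the last row, which is simulation only):

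| Assumed rates (placebo/100/300/600 mg) | Four-arm | 600 mg vs placebo |
|---|---|---|
| 30/30/30/50% | 56% | 53–55% |
| 30/35/43/50% | 43% | 53–55% |
| 30/50/50/50% | 52–54% | 53–55% |
| 30/40/50/55% | 63% | 73–74% |

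In the last row the other two pairs have about 18% (100 mg) and 54–55% (300 mg), so there the four-arm test is the more powerful.

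**Strata** (one dose against placebo, two equal strata). With no treatment effect, the unstratified test rejects in 3.7% of trials for stratum rates 15%/45% and in 2.1% for 10%/60%; Mantel-Haenszel stays near 5%. Power, unstratified against stratified, is 54.6% against 55.4% for a mild stratum effect (placebo 20%/40%, active 40%/60%) and 55% against 65% for a strong one (placebo 10%/50%, active 25%/75%).

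**Cost in error rate.** Two thresholds × three scores = 6 tests; with three doses, 18. For one endpoint with no true effect, three tests sharing a placebo arm give at least one false positive in 11.5–14.2% of simulated trials (common rate 30% or 50%, 50 or 55 per arm). Independent tests would give 1 − 0.95³ = 14.3%.

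**Missing Week 24.** Take 55 randomised per arm and 15 against 25 responders. Counting missing as non-response gives 27.3% against 45.5%, p = 0.048. With 3 against 10 missing, observed cases give 15/52 = 28.8% against 25/45 = 55.6%, p = 0.008. With 10 against 3 missing they give 33.3% against 48.1%, p = 0.141.

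**The case against.** The strongest reply is that the appendix code is only illustrative: SAP 8.2 lets it be changed. For Marsh, the governing text already says active against placebo, so this is a mismatch between text and code that a programmer could resolve. That stands in part. It does not rescue the responder test, whose text offers no comparison to return to.

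Responder rates will be tabulated by arm, overall and by subgroup, and the subgroups in SAP 8.6.1.6 are the two randomisation factors. A reader can therefore set each dose beside placebo, but only descriptively.

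Four stronger readings are tempting, and the documents do not support them:

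- **That the four-arm test loses power.** This depends on the response pattern; the documents give no rates.
- **That ignoring the strata biases the result or inflates false positives.** The unstratified test is conservative, and with a mild stratum effect the loss is negligible. The Abdominal stratum also does not measure baseline on the other domains.
- **That the plan discards dropouts and must count them as failures.** SAP 8.2.1 says "Denominators for percentages are the number of subjects with non-missing values in the pertinent analysis set and treatment group as appropriate", but that is a default for percentages and allows exceptions. No responder rule is stated, so exclusion is inferred from this default and from the usual behaviour of PROC FREQ. A Week 24 score is also missing whenever fewer than four diary days exist (SAP 8.2.2.1), so missing does not mean dropout. Counting every missing value as failure is a different assumption from the primary model's missing at random.
- **That responders establish meaningful change.** Protocol 8.2.6 gives that role to PGIS and PGIC.

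The protocol's exploratory section (9.4.4) is not legible, so a pairwise statement there cannot be excluded.

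**Conclusion.** The point holds as one of interpretability. As coded, both analyses are four-arm tests, and neither compares any dose with placebo, which is the aim in Protocol 4.2 and, for Marsh, in the SAP's own text. The four-arm coding alone causes this. Leaving out the randomisation factors is a separate and smaller weakness of precision, and the lack of a rule for missing Week 24 scores is a gap in specification, not a proven bias.

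The degrees of freedom and the text-code conflict follow from the documents without assumption. The worked examples, which show the coded test misleading in either direction, rest on assumed counts. Because the endpoints are exploratory and the code may be changed without amendment, severity is low to moderate.

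**What to change.** 1. **Responders (SAP 8.6.3 and 11.4).** State three comparisons, each dose against placebo. For each, use a CMH test stratified by VH:CD (<2, ≥2) and baseline Abdominal score (<3, ≥3), with a risk difference and 95% CI.
2. **Marsh (SAP 11.4).** Subset the CMH code to placebo plus one dose at a time, keep the baseline Marsh stratum, name the row-mean-scores statistic as the one reported, and correct the RESPONSE note to the three-level outcome.
3. **Missing Week 24, as a supplement only.** Show responder rates with missing counted as non-response beside the observed-case rates.

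The cost is a few sentences of SAP text and a WHERE clause. The real price is more tests: responder tests rise from 6 to 18 and the Marsh test from one to three, unadjusted under SAP 8.2, with about a 13% chance of at least one false positive per endpoint across three doses. Label these results exploratory.
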